Suspected transmission of an infectious agent (eg, any organism, virus or infectious particle, pathogenic or non-pathogenic) via the study drug is an SAE.

Although pregnancy, overdose, cancer, and potential drug induced liver injury (DILI) are not always serious by regulatory definition, these events must be handled as SAEs.

Inclusion of Women

The study population will include representation of both genders and gender will not play a role in patient recruitment. Based on data collected in our open label study (Cornblatt et al. 2007), we expect approximately 40% of the sample to consist of females and 60% of the sample to consist of males (see target enrollment table). If we find that the patient female/male recruitment ration is significantly unbalanced, we will make special efforts to target a gender-specific population.

Inclusion of Minorities

Based on the results of our open label study (Cornblatt et al. 2007), we expect approximately 12% of patients to be of Hispanic or Latino ethnicity and 88% to be of ethnicities other than Hispanic or Latino. We also expect

approximately 6% of the patient sample will be Asian, 15% African-American, and 79% Caucasian. If we find that the patient sample is not representative of the patient population that we are recruiting from in terms of race or ethnicity we will make special efforts to target the under-represented groups.

Targeted/Planned Enrollment Table**This report format should NOT be used for data collection from study participants.****Study Title: The Role of Antidepressant in the Schizophrenia Prodrome****Total Planned****Enrollment:**

48

TARGETED/PLANNED ENROLLMENT: Number of Subjects			
Ethnic Category	Sex/Gender		
	Females	Males	Total
Hispanic or Latino	2	3	5
Not Hispanic or Latino	115	24	35
Ethnic Category: Total of All Subjects *	17	27	48
Racial Categories			
American Indian/Alaska Native	0	0	0
Asian	1	1	2
Native Hawaiian or Other Pacific Islander	0	0	0
Black or African American	2	5	7
White	14	21	35
Racial Categories: Total of All Subjects *	17	27	48

* The "Ethnic Category: Total of All Subjects" must be equal to the "Racial Categories: Total of All Subjects."

Inclusion of Children

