While these first findings of a protective effect of antidepressants in prodromal individuals add to an intriguing line of primarily indirect evidence suggesting that antidepressants, which have a favorable risk-benefit ratio, may influence the development of psychosis, the lack of randomization and potential of prescriber bias reduce the interpretability of these early data. Therefore, we now propose to conduct a randomized, controlled 6-month pilot study comparing the antidepressant fluoxetine with the second generation antipsychotic aripiprazole in 48 subjects aged 12-25 years with at least moderate attenuated positive symptoms that developed within the past five years. Since transition to psychosis can occur at a relatively low rate over a very variable and potentially long time frame, and since discontinuation rates in long-term studies of putatively prodromal cohorts have been very high, we have designed a randomized, double-blind study focusing on intermediate outcomes, including the composite of all-cause-discontinuation and/or addition of a major psychotropic medication (see below), symptom change, safety, and adherence. The specific aims are:

Specific Primary Aim 1: To compare fluoxetine and aripiprazole on the likelihood of and time to all-cause discontinuation/need to add another psychiatric medication, symptomatic improvement, and adverse effects

Primary Hypothesis 1: Compared to aripiprazole, significantly fewer patients on fluoxetine will either discontinue treatment or require the addition of an antipsychotic, mood stabilizer, antidepressant or of >3 weeks of treatment with an anxiolytic/hypnotic

Secondary Hypothesis 1: Compared to aripiprazole, time to all-cause discontinuation or need to add another psychiatric medication (as defined above) will be significantly longer with fluoxetine

Secondary Hypothesis 2: Compared to aripiprazole, changes in attenuated positive, negative and general psychopathology will be similar with fluoxetine.

Secondary Hypothesis 3: Compared to aripiprazole, fluoxetine will be associated with significantly lower rates of adverse effects.

Specific Secondary Aim 1: To compare the effect of fluoxetine and aripiprazole on social and role functioning and subjective well-being in individuals at risk for schizophrenia.

Primary Hypothesis 1: Compared to aripiprazole, fluoxetine will lead to significantly greater improvement in social and role functioning.

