Adjunctive Therapies. Based on our previous experience with administration of fluoxetine and aripiprazole in prodromal patients, we expect the need for rescue medication to be relatively infrequent. However, adjunctive medication will be available to address clinically relevant, treatment emergent side effects. These include: benztrapine (up to 2 mg bid) for extrapyramidal symptoms (EPS) in case dose reduction is ineffective or undesired; lorazepam (up to 1 mg bid) to treat restlessness, anxiety or agitation, or to improve sleep; and propranolol (up to 20 mg tid) for akathisia. Moreover, when a patient develops $\geq 7\%$ weight gain, which triggers healthy lifestyle interventions involving simple education regarding diet and physical activity, and despite this exceeds 10% weight gain, metformin (500-2000 mg) will be offered. After the patient is symptom free for at least two weeks a slow withdrawal of the adjunctive medication will be attempted. Patients will also receive supportive psychotherapy by during regular medication visits. Needs based individual psychotherapy will be provided for crisis situations and in a time limited fashion (i.e., six sessions).

Assessments. Table 2 summarizes the proposed diagnostic, efficacy and safety assessments throughout the 24-week study. Subjects can still be assessed ± 7 days of their proposed assessment date in the event that there are unable to come in at the proposed time.

The ACISR Trials Operation Unit maintains a cadre of trained raters and assessors with experience in the majority of measures utilized, the Clinical Assessment Strategies Unit has been instrumental in the development of individual assessment measures of patient function, and the Adverse Event Unit provides expertise in the assessment and management of drug-induced adverse events, of particular importance in this population who may be more sensitive to drug side effects, and which may predict non-adherence.

Patients who discontinue the assigned medication or who initiate treatment with a medication that is not allowed as per the protocol will have an unscheduled study termination visit, but patients will be assessed at

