Specific Primary Aim 1. *To compare fluoxetine and aripiprazole on time to all-cause-discontinuation/need to add another psychotropic agent, prodromal symptom change and adverse effects in prodromal individuals.* Binary outcomes, such as the primary composite outcome variable and the dichotomized presence of specific side effects (i.e., present=moderate severity or higher) or non-adherence, will be analyzed using chi squared test or Fischer's Exact test, as necessary. Standard methods of survival analysis (Kaplan-Meier product-limit method, logrank test, Cox proportional hazards regression) will be applied to the secondary, time dependent variable "time until all-cause-discontinuation/need to add another psychotropic". If during the trial a subject is lost to follow up, that subject's data will be "censored" at the week of dropout. Cox proportional hazards regression model will be used to determine which factors (if any) are predictive of all cause discontinuation. In addition to the ITT analyses, we will also conduct a sensitivity analysis using only data from subjects as long as they remained on the assigned treatment, censoring data at the week of treatment discontinuation.

Repeated measures analysis of variance (RMANOVA) using a mixed models approach (SAS PROC MIXED, SAS Institute, Cary, NC) will be used to examine the longitudinal and between-drug patterns in continuous outcomes, such as psychopathology rating scores and severity of side effects. In case of relevant missing data, PROC MIXED will be able to model the data despite the missing values. RMANOVA using the mixed models approach will be utilized to analyze changes in weight, BMI and HOMA-IR (using the log ratio transformation). The method of generalized estimating equations (GEE) will be used to analyze ordinal data, such as Barnes and Simpson-Angus scores.

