Recently, the Food and Drug Administration (FDA) issued a public health advisory concerning a possible link between worsening depression and emergence of suicidal ideation or behavior in patients treated with certain antidepressant medications, including but not limited to sertraline. The FDA has not concluded that these drugs cause worsening depression or suicidality: worsening of symptoms could be due to the underlying problem or might be a result of drug therapy. As a result, we will carefully monitor patients in this trial for possible worsening of depression or suicidality, especially at the beginning of therapy or when the dose either increases or decreases.

We will ask study participants to let us know immediately if they feel worse in any way, at any time during treatment. If suicidal thoughts begin or worsen, associated with taking medication, they will be urged to call the study doctor immediately. It is very important that participants do not abruptly stop taking the medication without first discussing this with the study doctor as suddenly stopping these medications may be followed by withdrawal symptoms or by a return of the depressive feelings.

Common, non-serious side effects for aripiprazole are extra-pyramidal symptoms (including tremor, stiffness, and restlessness), sedation, dizziness, either weight loss or weight gain, hyperglycemia (high blood sugar), nausea, dry mouth, headache and sexual side effects.

Two potentially serious but infrequent side effects have been associated with aripiprazole:

Tardive dyskinesia (TD), which includes abnormal movements of the mouth, face, tongue, arms or legs. For some people, the movements continue even if the medication is stopped. The extent to which risperidone causes TD has not yet been determined, but there is evidence that it is as low as 1% per year of treatment. This rate is as low as or lower than the TD rates for other FDA-approved medications in the same class.

Neuroleptic malignant syndrome (NMS), a very rare, but potentially serious disorder characterized by neurological changes, fever and other symptoms, has been reported with risperidone. If NMS develops, it typically does so shortly after medication is started. NMS is easily treatable and is readily detected by clinical evaluation that includes vital signs, the testing of muscle tone and blood tests if indicated. These evaluations will be performed at each psychiatric visit.

2. Adequacy of Protection Against Risks

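### EPS and akathisia are compared from ratings that benztropine or propranolol may have improved, and the analysis takes no account of the start of either drug

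*Combined protocol and SAP*

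**What the plan says.** Secondary Hypothesis 3 under Specific Primary Aim 1 is directional: "fluoxetine will be associated with significantly lower rates of adverse effects".

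Research Plan, Adjunctive Therapies, states that "adjunctive medication will be available to address clinically relevant, treatment emergent side effects". Benztropine is allowed "for extrapyramidal symptoms (EPS) in case dose reduction is ineffective or undesired", and the list also includes "propranolol (up to 20 mg tid) for akathisia". Lorazepam is allowed for restlessness, anxiety, agitation or sleep, and metformin once weight gain passes 10%. Withdrawal of an adjunct is attempted after at least two symptom-free weeks. The section expects rescue medication to be needed relatively rarely and gives no rate.

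Analytic Plan, Specific Primary Aim 1, analyses the same effects in two ways. Chi-squared or Fisher's exact tests are applied to the "dichotomized presence of specific side effects (i.e., present=moderate severity or higher"), with no visit or time window given. Generalized estimating equations (GEE) "will be used to analyze ordinal data, such as Barnes and Simpson-Angus scores". The one sensitivity analysis censors at the week the assigned treatment is discontinued.

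Human Subjects, Risks to the Subjects, says: "Common, non-serious side effects for aripiprazole are extra-pyramidal symptoms (including tremor, stiffness, and restlessness"). The fluoxetine list in the same section contains neither EPS nor restlessness.

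**The concern.** A Barnes or Simpson-Angus score taken on propranolol or benztropine describes the treated state. If the drug works, a patient whose akathisia or EPS was bad enough to be treated can score like one who never had it. Nothing in the analysis separates the two. Starting either drug is not a side-effect event, there is no covariate or rule for later ratings, and no table of adjunct use by arm is planned.

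On the protocol's own side-effect lists, these two drugs should be needed mostly in the aripiprazole arm. Any masking would then shrink the difference that Secondary Hypothesis 3 looks for and make aripiprazole appear better tolerated than it was. The trial is a pilot whose estimates are meant to inform the design of a larger one, so a diluted side-effect difference could be carried forward.

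**Working it through.** **1. The plan's own figure.** The only stated power is 82%, for the primary composite. With rates of 65% and 25%, n = 24 per arm and two-sided alpha 0.05:

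- power = Φ[(d − 1.96·SE0)/SE1], where SE0 = √(2·p̄(1−p̄)/n) and SE1 = √(p1(1−p1)/n + p2(1−p2)/n)
- d = 0.40 and p̄ = 0.45, so SE0 = 0.1436 and SE1 = 0.1315
- power = Φ[(0.40 − 0.2815)/0.1315] = Φ(0.90) = 81.6%

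The 82% reproduces, and this point does not affect it. No power or expected rate is given for any side-effect outcome.

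**2. Where a start of benztropine or propranolol could enter the analysis.**

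- Binary side-effect outcomes: severity rating only.
- GEE on Barnes and Simpson-Angus: scores only.
- Sensitivity analysis: triggered by stopping the assigned drug. A patient given an adjunct stays on the assigned drug and is not censored.
- Primary composite: Primary Hypothesis 1 counts antipsychotics, mood stabilizers, antidepressants and more than three weeks of an anxiolytic or hypnotic. The Assessments section speaks more broadly of a psychotropic added to the daily regimen, prn use excluded. Neither names benztropine or propranolol. Even if daily use were counted there, it would not be a side-effect outcome.

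**3. When a rating could miss the effect.** Table 2 schedules SAFTEE, Barnes and Simpson-Angus at weeks 0, 1, 2, 3, 4, 6, 8, 12, 16, 20 and 24.

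- Repeated scores: every rating made on the adjunct is used, however frequent the visits.
- Binary outcome read at a fixed visit: a case treated before that visit can be scored absent.
- Binary outcome read as ever moderate or worse: early cases will usually be caught. After week 8 visits are 4 weeks apart, or up to 4 + 1 + 1 = 6 weeks with the ±7-day window. Dosing is flexible from week 4, so onset and treatment can both fall between ratings.

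**4. Illustration of size (assumed inputs).** The documents supply only n = 24 per arm. One missed aripiprazole case is 1/24 = 4.2 points. Let pA and pF be the true rates and m the share of aripiprazole cases scored absent, with none masked on fluoxetine. Then observed difference = pA(1 − m) − pF, and power follows from the formula in step 1.

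| Assumed pA vs pF | m = 0 | m = 25% | m = 50% | m = 75% |
|---|---|---|---|---|
| 40% vs 10% | 30 points, 68% | 20 points, 41% | 10 points, 16% | 0 points, 2.5% |
| 50% vs 10% | 40 points, 88% | 27.5 points, 62% | 15 points, 27% | 2.5 points, 5% |
| 30% vs 5% | 25 points, 63% | 17.5 points, 42% | 10 points, 21% | 2.5 points, 5% |

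With Fisher's exact test, the first three powers in the 40% vs 10% row are 60%, 31% and 10%. In that row, m = 25% means 0.25 × 0.40 × 24 = 2.4 patients. A few masked cases would matter in arms this small, but nothing in the documents says how many there would be.

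**The case against.** A reader might infer that harms are in fact under-recorded, and that all four adjuncts hide side effects mainly in the aripiprazole arm. The documents do not support that.

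- **Under-recording is possible, not shown.** Adjuncts are for effects already judged clinically relevant, and benztropine comes in only where reducing the dose has not worked or is not wanted. The effect has usually been noticed first. Ratings are weekly through titration, so an ever-moderate outcome would catch many cases. The documents do not say that SAFTEE covers only the day of the visit.
- **Lorazepam is not specific to one arm.** It is also given for sleep, and insomnia is a listed fluoxetine side effect. More than three weeks of it already counts in the primary composite.
- **Metformin follows a gain above 10%.** Weight is measured at every visit from week 0, so that gain should already be on record. Only later weight, BMI and HOMA-IR values could be affected.
- **Observed ratings are a legitimate choice.** Using ratings whatever adjunct is taken is a treatment-policy reading that fits the stated ITT principle. Deleting GEE data after adjunct start would depend on the outcome and could itself bias the comparison.
- **The bias works against the trial's own hypothesis**, which is secondary in a 48-patient pilot.

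All of this stands. It narrows the point to EPS and akathisia and leaves the size unknown. It does not supply the missing rule: the binary outcome has no window, and the start of a drug given for EPS or akathisia still counts for nothing in the side-effect comparison.

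**Conclusion.** The point holds for EPS and akathisia. Ratings taken on benztropine or propranolol may understate these effects, probably more under aripiprazole, and so pull Secondary Hypothesis 3 toward no difference. The masking is clearest for the repeated Barnes and Simpson-Angus scores. For the binary outcome it arises if a fixed visit is analysed, or if onset and treatment fall between the four-weekly visits after week 8.

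The size cannot be computed. The table above rests on assumed side-effect rates and masked shares, and the expectation of infrequent use points to its left-hand columns. The direction rests on the protocol's two side-effect lists. The likely cost is a diluted difference and lost power, not a false claim in favour of fluoxetine. The remedy is cheap enough to be worth making despite that uncertainty.

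**What to change.** 1. Define each binary side-effect outcome over all post-baseline visits: present if rated moderate or higher at any visit, or if an adjunct was started for that effect (benztropine for EPS, propranolol for akathisia).
2. Tabulate adjunct starts by arm and indication, including lorazepam and metformin.
3. State that the main analysis of Barnes, Simpson-Angus, weight, BMI and HOMA-IR uses observed values whatever adjunct is taken (treatment policy). Any analysis limited to values before adjunct start should be a sensitivity analysis only, with its missing-data assumption stated: standard GEE needs data missing completely at random, and removal at adjunct start depends on the outcome.

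The cost is a few sentences in the Analytic Plan and one derived variable, provided the medication record gives start date and indication. Patient care does not change. The downside is that some mild but treated effects will count as present.

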Recruitment. We will recruit patients utilizing the ACISR Trials Operation Unit, which has developed recruitment strategies within the child and adolescent as well as adult outpatient and emergency room services at Zucker Hillside Hospital, with additional referrals from the inpatient units. In addition, to increase the pool of potentially eligible patients, our ACISR maintains a Research Network that will liaise with local community mental health clinics offering a screening program for potentially prodromal symptoms in the clinic clientele. We will approach mental health clinics associated with Queens Child Guidance Center (5 clinics), North Shore Child Guidance Center (3 clinics), South Shore Child Guidance Center, Peninsula Counseling Center, Pederson-Krag Center, as well as the outpatient clinics of Kings County Hospital and Stony Brook Hospital. Finally, we are setting up a collaboration with the St Luke's Roosevelt hospital PEER program in Manhattan, a dedicated first episode and prodromal psychosis outpatient program that just received 2-year structural funding from the van Ammeringen Foundation. Furthermore, we are in contact with the psychiatry department at SUNY Downstate. St. Luke's Roosevelt and, potentially SUNY Downstate, will become sites for this study and will need to obtain their own IRB approval. The other mental health clinics will be utilized as referral sources. Thus, while presentations and outreach will take place, patients will not be assessed and treated at these centers; treatment will reside at the treatment sites, namely Zucker Hillside Hospital, St. Luke's Medical Center and, possibly SUNY Downstate.

Medication Schedule. Randomization codes to either aripiprazole or fluoxetine will be provided by the NSLIJ biostatistics group. To increase homogeneity and assure treatment with a clinically effective dose, patients will undergo a fixed titration phase during the first three weeks, with the option to slow or halt the titration or

Table 1. Titration	Wk 0/Wk 1	Wk 1/2	Wk 2/3	Week 4-Week 24
	Fixed	Fixed	Fixed	Flexible Dosing, Range
Fluoxetine	10 mg	10 mg	20 mg	10mg – 60mg
Aripiprazole	2 mg	5 mg	10 mg	5mg – 30mg

decrease the target dose if intolerance develops (Table 1). After 3 weeks, dosing will be flexible and left up to clinical choice and need.

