Specific Secondary Aim. *To compare the effect of fluoxetine and aripiprazole on social and role functioning and subjective well-being in individuals at risk for schizophrenia.* As for primary aim 1, repeated measures analysis of variance (RMANOVA) using a mixed models approach (SAS PROC MIXED, SAS Institute, Cary, NC) will be used to examine the longitudinal and between-drug patterns in these continuous outcomes. In addition, the correlation between social and role functioning scale score changes and changes in attenuated positive and negative symptoms scores will be analyzed using the Bland and Altman methodology. Likewise, correlations between changes in subjective well being and psychopathology scores as well as side effect change scores will be analyzed using that same methodology.

Table 2: Assessment Timetable

Weeks/ Months	Pre-screen	Screen	Wk 0	Wk 1	Wk 2	Wk 3	Wk 4	Wk 6	Wk 8	Wk 12	Wk 16	Wk 20	Wk 24
Assessments													
MD													
Physical Examination		+											
SAFTEE (side effects)			+	+	+	+	+	+	+	+	+	+	+
Psychometrician													
Kid-SCID		+											
Premorbid Adjustment		+											
IQ Test		+											
SIPS/SOPS	+	+	+	+	+	+	+	+	+	+	+	+	+
BPRS, SANSS			+	+	+	+	+	+	+	+	+	+	+
CGI			+	+	+	+	+	+	+	+	+	+	+
Hamilton Scale for Depression			+	+	+	+	+	+	+	+	+	+	+
Young Mania Rating Scale			+	+	+	+	+	+	+	+	+	+	+
Drug Attitude Inventory			+				+		+	+	+		+
Social Functioning and Role Functioning Scale			+							+			+
Subjective Wellbeing Scale (SWN-K, Naber 1995)			+							+			+
Research Technician													
Simpson-Angus (EPS)			+	+	+	+	+	+	+	+	+	+	+
Barnes Akathisia			+	+	+	+	+	+	+	+	+	+	+
AIMS (Dyskinesia)			+	+	+	+	+	+	+	+	+	+	+
Vital signs/Weight			+	+	+	+	+	+	+	+	+	+	+
Fasting blood tests (CBC, comprehensive metabolic panel, glucose, insulin, lipid profile, TSH, LFTs) and urine analysis		+ ^a	+					+		+			+
Study medication level									+		+	+	
Pregnancy test (urine ^d or serum)			+	+				+		+	+		+
Urine toxicology			+	+				+		+	+		+
DNA blood draw & storage (optional)				+ ^b									
Brain Derived Neurotrophic Factor			+	+				+		+	+		+

^a can be non-fasting, no insulin and lipid level required; ^b can be obtained at any time during the study if needed; ^c SIPS can be used from Pre-screen if screening done within 2 days.

^d when subject outpatient, urine test will be used, when inpatient then we will use serum pregnancy test already for in unit.

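### The ±7-day visit allowance equals the weekly spacing of the early visits, so neighbouring visits can share a day and the first on-drug safety check can fall on day 14

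*Combined protocol and SAP*

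**What the plan says.** The Assessments section of the Research Plan gives one allowance for all visits: a subject may be "assessed ± 7 days of their proposed assessment date in the event that there are unable to come in at the proposed time". No narrower window is set for the early visits, and no minimum gap between visits is stated.

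Table 2 schedules visits at Weeks 0, 1, 2, 3, 4, 6, 8, 12, 16, 20 and 24. Participant Compensation pays for Weeks 1, 2, 3 and 4 as separate visits, so they are meant to be distinct. In Table 2 the SAFTEE side-effect rating and the "Hamilton Scale for Depression" are marked at Week 0 and at every later visit. Protection against risk names the suicidality item of the depression scale as the screen, with a formal suicide-severity assessment if it is above zero.

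Under Medication Schedule, "patients will undergo a fixed titration phase during the first three weeks", with the option to slow, halt or reduce if intolerance develops. Table 1 gives aripiprazole 2, 5 and 10 mg and fluoxetine 10, 10 and 20 mg for the three steps. It does not say whether a step is taken on the calendar day or at the visit.

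Risks to the Subjects commits to monitoring for "possible worsening of depression or suicidality, especially at the beginning of therapy or when the dose either increases or decreases". On neuroleptic malignant syndrome (NMS), listed under aripiprazole, it says "If NMS develops, it typically does so shortly after medication is started", and of the evaluations that detect it, "These evaluations will be performed at each psychiatric visit".

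**The concern.** The protocol's early safety monitoring is built on visits. The suicidality screen, the side-effect rating and the NMS evaluations all take place there. The Assessments section also describes adverse-event assessment as "of particular importance in this population who may be more sensitive to drug side effects, and which may predict non-adherence". A tolerance as wide as the spacing between visits works against the commitment to watch most closely at the start of treatment and at dose changes. The first of these checks on drug can come a week late, in patients aged 12 to 25, and still count as on schedule.

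There is also a smaller data issue. The mixed models under Specific Primary Aim 1 describe the course of symptoms and side-effect severity over time. Ratings labelled as different weeks but made on one day add no separate information on that early course.

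**Working it through.** **The plan's own figure.** The only stated power is 82%, for 65% against 25% with 24 per arm at two-sided 0.05. The pooled normal approximation gives 81.6%, so the figure reproduces. It does not depend on visit timing and is not affected by this point.

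**Inputs.** Nominal day = 7 × week (Table 2). Window = nominal day ± 7 (Assessments). Dose steps are read from Table 1 as starting at nominal days 0, 7 and 14.

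**Windows as written.**

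| Visit | Any in-window day | On time or late only |
|---|---|---|
| Week 1 | 0–14 | 7–14 |
| Week 2 | 7–21 | 14–21 |
| Week 3 | 14–28 | 21–28 |
| Week 4 | 21–35 | 28–35 |
| Week 6 | 35–49 | 42–49 |
| Week 8 | 49–63 | 56–63 |
| Week 12 | 77–91 | 84–91 |

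- Weeks 1 and 2 share days 7 to 14, which is 8 calendar days. Weeks 2 and 3, and Weeks 3 and 4, overlap by the same amount. Day 14 is in window for Weeks 1, 2 and 3 at once.
- Weeks 4 and 6 touch only on day 35, and Weeks 6 and 8 only on day 49. Weeks 8 and 12 are 77 − 63 = 14 days clear.
- Of the 10 post-baseline visits, 6 can share a day with a neighbour if any in-window day counts (Weeks 1, 2, 3, 4, 6, 8). If only on-time or late visits count, it is 4 (Weeks 1 to 4).
- Latest in-window first on-drug check, both arms: 7 + 7 = day 14, against day 7 planned.

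**Dosing, two readings.**

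- *Steps follow the calendar.* Aripiprazole goes to 5 mg on day 7, so the first check can come up to 14 − 7 = 7 days after the increase. Fluoxetine stays at 10 mg until nominal day 14, so no fluoxetine increase precedes the check.
- *Steps follow the visit.* No increase precedes the check. Time at 5 mg is the Week 2 day minus the Week 1 day, planned 14 − 7 = 7. For on-time or late visits it runs from 14 − 14 = 0 to 21 − 7 = 14 days. The zero requires one attendance to count as two titration visits, which no section permits.

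**With ±3 days at Weeks 1 to 4.** The windows become days 4–10, 11–17, 18–24 and 25–31, with no shared day. Week 6, still at ±7, opens on day 35, 4 days after Week 4 closes. The latest in-window first check is day 10. Calendar dosing leaves at most 10 − 7 = 3 days at 5 mg before the check. Visit-based dosing, for on-time or late visits, leaves 14 − 10 = 4 to 17 − 7 = 10 days at 5 mg. The single-day touch of Weeks 6 and 8 on day 49 remains unless those two visits use ±6 (days 36–48 and 50–62).

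**The case against.** The allowance is an exception for patients who cannot come, not routine scheduling. It decides whether a late assessment is accepted, not when a patient is available: someone who cannot attend until day 14 is first seen on day 14 under any window. That stands. The narrower window mainly makes the delay visible as out of window, and the protection against an unchecked step has to come from a dosing rule. The documents give no rescheduling rate, so the frequency of the problem is unknown.

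A reader might infer that the plan lets aripiprazole be raised before anyone has checked the patient. The documents do not support that. Table 1 labels its steps by visit weeks, and Adjunctive Therapies refers to supportive psychotherapy given "during regular medication visits", so visit-based dosing is at least as plausible. Even under calendar dosing, 5 mg is the bottom of the later flexible range. Nor does the antidepressant suicidality warning coincide with an early fluoxetine increase, because none is scheduled at Week 1.

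A reader might also infer that early monitoring is absent. It is not. Participants are asked to report any worsening at once, titration can be slowed or halted, and exit rules apply. The exit rules use the CGI-I and BPRS. Table 2 schedules the CGI and BPRS at the same visits, so those ratings shift with the window; self-report does not. NMS is described as very rare, and the text there speaks of reports with risperidone, so it should not carry much weight.

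Finally, the overlaps involving Weeks 6 and 8 need one visit a full week late and the next a full week early. An early rating lost to a merged visit is something the planned mixed model can accommodate.

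**Conclusion.** The point holds as a minor one. A stated rule, not a missing detail, lets neighbouring visits in Weeks 1 to 4 coincide and lets the first scheduled on-drug side-effect and suicidality check fall on day 14 instead of day 7, in both arms and under either dosing reading. That sits poorly with the protocol's commitment to close monitoring at the start of therapy and at dose changes.

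The date arithmetic rests only on the stated window and schedule. The further consequence, up to 7 days on aripiprazole 5 mg before any scheduled on-drug check, holds only if steps follow the calendar, which the protocol leaves open. The primary composite outcome, its power and alpha do not change, and no claim is made about how often visits will move.

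**What to change.** 1. Use at most ±3 days for Weeks 1 to 4 and keep ±7 days for later visits. Using ±6 at Weeks 6 and 8 is optional and only removes the single-day touch on day 49.
2. State that each blinded titration step is taken only after the side-effect and HAM-D suicidality assessment for the current step is completed. Apply this in both arms whether or not the dose changes: fluoxetine has no increase at Week 1, so a rule worded around dose increases would treat the arms differently. A late visit delays the step, and one attendance cannot count as two titration visits.

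The two parts do different work. The window separates the early visits and makes a first check after day 10 out of window. The titration rule prevents an unchecked step, including when a patient cannot come until day 14.

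One limit remains. Under ±3 days, a late visit followed by an early one can still be 1 day apart (days 10 and 11); with on-time or late visits the shortest gap is 4 days.

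The cost is protocol wording, a few more recorded out-of-window early visits, and slightly longer titration for some patients.
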